9.3 Selection of Study Population

At least 850 subjects with EAD including MCI due to AD and the early stages of mild AD will be enrolled across up to approximately 250 centers worldwide (revised per Amendment 06). Randomization will be stratified according to region (7 levels), clinical dementia staging, with no more than approximately 25% of the randomized subjects diagnosed with the early stages of mild dementia due to AD, and concurrent AD medication use. (revised per Amendments 01 and 02) Subjects who do not meet all of the inclusion criteria or who meet any of the exclusion criteria will not be eligible to receive study drug.

9.3.1 Inclusion Criteria

Subjects must meet all of the following criteria to be included in this study:

Core Study

1. MCI due to AD or Mild AD according to the National Institute of Aging – Alzheimer’s Association (NIA-AA) core clinical criteria and must have all of the following at Screening: (revised per Amendment 04)
 - a. MMSE score equal to or greater than 24
 - b. CDR global score of 0.5
 - c. CDR Memory Box score of 0.5 or greater
2. A history of subjective memory decline with gradual onset and slow progression over the last 1 year before Screening; this MUST be corroborated by a study partner
3. Cognitive impairment of at least 1 SD from age-adjusted norms in total recall or delayed recall on the ISLT.
4. Positive biomarker for brain amyloid pathology as indicated by at least 1 of the following:
 - a. PET assessment of amyloid imaging agent uptake into brain. Note: amyloid PET screens will be performed according to local regulatory guidelines and thus may be restricted for those subjects who are not suitable for LP to obtain CSF for testing of eligibility.
 - b. CSF AD assessment (eg, tau: A β (1-42) ratio) (revised per Amendment 04)

NOTE: Subjects may undergo both the amyloid PET and CSF assessments, but need a positive amyloid result in only 1 of the 2 procedures to confirm eligibility. Subjects who consent to amyloid PET or CSF for eligibility purposes are not required to participate in the amyloid PET or CSF longitudinal substudies. Use of a historical amyloid positive PET (conducted within 12 months before the planned date of randomization) is acceptable for determination of eligibility but will not suffice for the baseline assessment if the subject wishes to consent to the amyloid PET longitudinal substudy. The historical imaging data must be made available to the sponsor. Historical CSF samples, if collected, processed, and stored under appropriate conditions and approved by the sponsor, may be analyzed to determine CSF amyloid positivity. (revised per Amendments 04 and 06).
5. Male or female subjects between 50 and 85 years of age, inclusive at the time of consent
6. If receiving an AChEI or memantine or both for AD, must be on a stable dose for at least 12 weeks before Randomization. Treatment-naïve subjects with AD can be entered into the study.
7. Subjects must have been on stable doses of all other (ie, non-AD related) permitted concomitant medications for at least 4 weeks before Randomization, except for medications which are administered as short courses (eg, up to 3 weeks unless discussed and agreed with the medical monitor) of treatment (eg, anti-infectives, oral steroids) or which are to be used on a Pro re nata (PRN) basis. Subjects who require a short course of treatment, such as anti-infectives or oral steroids, may be randomized once the acute illness has completely resolved, even if the concomitant medication continues. (revised per Amendment 01)
8. Must have an identified study partner (defined as a person able to support the subject for the duration of the study and who spends at least 8 hours per week with the subject). The study partner must be literate and able to provide written informed consent. (revised per

Amendment 04) In addition, this person must be willing and able to provide follow-up information on the subject throughout the course of the study. This person must, in the opinion of the investigator, spend sufficient time with the subject on a regular basis such that they can reliably fulfill the requirements of being a study partner. A study partner need not be living in the same residence with the subject. For such a study partner not residing with the subject, the investigator has to be satisfied that the subject can contact the study partner readily during the times when the study partner is not with the subject. Study partners need to provide input to the following assessments: CDR, FAQ, EQ-5D, QOL-AD, Zarit's Burden Interview, NPI-10, and the clinical assessment of suicidality. (revised per Amendment 01) Consideration can occur for the investigator to decide whether the study partner can provide information over the telephone or whether the study partner must attend the study visits in person with the subject.

9. Provide written informed consent. Subjects must, in the investigator's judgment, have the capacity to consent (capacity to consent should be determined in accordance with applicable professional standards and local laws/regulations). (revised per Amendment 04)

For inclusion criteria specific to the Extension Phase, refer to [Appendix 5 in Section 12](#).

9.3.2 Exclusion Criteria

Subjects who meet any of the following criteria will be excluded from this study:

1. Females who are breastfeeding or pregnant at Screening or Baseline (as documented by a positive beta-human chorionic gonadotropin test. A separate baseline assessment is required if a negative screening pregnancy test was obtained more than 72 hours before the first dose of study drug. Females of child-bearing potential who:
 - within 28 days before study entry, did not use a highly effective method of contraception, which includes any of the following:
 - total abstinence (if it is their preferred and usual lifestyle)
 - an intrauterine device or intrauterine hormone-releasing system
 - an oral contraceptive (Subject must be on a stable dose of the same oral contraceptive product for at least 28 days before dosing and throughout the study and for 28 days after study drug discontinuation.)
 - have a vasectomized partner with confirmed azoospermia
 - do not agree to use a highly effective method of contraception (as described above) throughout the entire study period and for 28 days after study drug discontinuation.

For sites outside of the European Union, it is permissible that if a highly effective method of contraception is not appropriate or acceptable to the subject, then the subject must agree to use a medically acceptable method of contraception, ie, double-barrier methods of contraception such as condom plus diaphragm or cervical/vault cap with spermicide.

NOTE: All females will be considered to be of child-bearing potential unless they are postmenopausal (amenorrhic for at least 12 consecutive months, in the appropriate age

- group, and without other known or suspected cause) or have been sterilized surgically (ie, bilateral tubal ligation, total hysterectomy, or bilateral oophorectomy, all with surgery at least 1 month before dosing)
2. Any condition that may be contributing to cognitive impairment above and beyond that caused by the subject's AD
 3. Subjects with a history of seizures within 5 years of Screening or subjects with disturbance likely to be due to seizures within 5 years of Screening
 4. History of transient ischemic attacks (TIA) or stroke within 12 months of Screening
 5. Modified Hachinski Ischemia Score greater than 4 at Screening
 6. Any of the following psychiatric symptoms:
 - Psychiatric diagnosis or symptoms, (eg, hallucinations, major depression, or delusions) that, in the opinion of the investigator, could interfere with study procedures
 - Has a “yes” answer to C-SSRS suicidal ideation items 4 or 5, or any suicidal behavior within 6 months before Screening, at Screening, or at the Randomization Visit, or has been hospitalized or treated for suicidal behavior in the past 5 years before Screening
 7. Have any contraindications to MRI scanning, including cardiac pacemaker/defibrillator, ferromagnetic metal implants (eg, in skull and cardiac devices other than those approved as safe for use in MRI scanners) or
 - Have any evidence of other clinically significant lesions that could indicate a dementia diagnosis other than AD on brain MRI at Screening.
 - Exhibit other significant pathological findings on central read of the brain MRI at Screening, including but not limited to: an area of superficial siderosis; evidence of cerebral vasogenic edema; evidence of cerebral contusion, encephalomalacia, aneurysms, vascular malformations, or infective lesions; evidence of multiple infarcts; evidence of stroke involving a major vascular territory; severe small vessel or diffuse white matter disease as defined by a score of 3 on the age-related white matter changes score ([Wahlund, et al., 2001](#)); space occupying lesions; or brain tumors (however, lesions diagnosed as meningiomas or arachnoid cysts and less than 1 cm at their greatest diameter need not be exclusionary). (revised per Amendments 04 and 06)
 8. Subjects who have a history of moderate to severe hepatic impairment (eg, Child-Pugh Class B or C). Any 2 of the following criteria at Screening would exclude the subject: $\text{INR} \geq 1.7$; $\text{bilirubin} \geq 1.5 \times \text{ULN}$; $\text{albumin} < \text{LLN}$; ascites or hepatic encephalopathy. Please note that a single significant abnormality could meet criteria for moderate impairment. (revised per Amendment 02)

9. Results of laboratory tests conducted during Screening that are outside the following limits:

- Absolute lymphocyte count (ALC) below Lower Limit of Normal (LLN) or below 800 per mm³ (whichever is higher); ALC will be derived from the complete blood count (CBC) with differential representing the normal lymphocytes (with atypical lymphocytes removed and presented as a separate count if they are present) and calculated by the white blood cell count × percentage of lymphocytes. (revised per Amendments 01 and 02)
- Thyroid stimulating hormone (TSH) above normal range. Other tests of thyroid function with results outside the normal range should only be exclusionary if they are considered clinically significant by the investigator (this applies to all subjects whether or not they are taking thyroid supplements)
- Abnormally low (below LLN) serum Vitamin B12 levels (if subject is taking Vitamin B12 injections, level should be at or above the LLN). Levels of Vitamin B12 may be confirmed with reflex testing to include methylmalonic acid (MMA) analysis, if available in region. (revised per Amendment 06)

10. Subjects at risk of increased risk of infection, specifically:

- Subjects with chronic viral hepatitis. Subjects with a history of chronic viral hepatitis C may be included if they meet the following requirements:
 - 1) evidence of treatment with direct antiviral combination therapy
 - 2) evidence of sustained virological response at least 12 weeks post-treatment

The inclusion of subjects with a history of chronic viral hepatitis C must be discussed and agreed with the medical monitor. (revised per Amendment 04)

- A history of active tuberculosis disease (TB), a history of ophthalmic shingles or a history of ocular herpes simplex virus (HSV) infection (revised per Amendment 04)
- Any active infection within the last 4 weeks before randomization. For such cases, the timing of randomization can be extended (up to 4 weeks) to allow the infection to resolve
- Any immunological disease which is not adequately controlled, or which requires treatment with biologic drugs during the study. History of immunoglobulin deficiency or other immunodeficiency disorders (including subjects known to be HIV positive)

11. Have received any live vaccine/live attenuated vaccine in the 3 months before randomization (revised per Amendment 01)

12. Any chronic inflammatory disease that is not adequately controlled or that requires systemic immunosuppressive or immunomodulatory therapy. (revised per Amendment 04)

NOTE: The following subjects do not need to be excluded:

- Subjects with seasonal or perennial allergic rhinitis, asthma, or chronic obstructive pulmonary disease where the condition is considered to be stable and adequately controlled by inhaled steroids.
- Hashimoto's thyroiditis but who are stable on thyroid replacement therapy and not on systemic immunosuppressive therapy.
- Cutaneous manifestations of immunological disease that do not require systemic immunosuppressive therapy or systemic immunomodulatory therapy (ie, topical steroid treatment is permitted)

13. Any other clinically significant abnormalities, such as:

- Physical examination or vital signs at Screening or Baseline which in the opinion of the investigator require further investigation or treatment or which may interfere with study procedures or safety. (revised per Amendment 04)
- Laboratory tests or ECG at Screening that in the opinion of the investigator require further investigation or treatment or may interfere with study procedures or safety. (revised per Amendment 04)
- Other medical conditions (eg, cardiac, respiratory, gastrointestinal, psychiatric, renal disease) which are not adequately and stably controlled, or which in the opinion of the investigator(s) could affect the subject's safety or interfere with the study assessments (revised per Amendment 02)
- Illiteracy, or severe visual or hearing impairment that would prevent the subject from performing psychometric tests accurately (revised per Amendment 01)

14. A prolonged QTcF interval (QTcF greater than 450 ms according to central reading at Screening). (revised per Amendment 04) If the QTcF machine read is greater than 440 ms on the first single 12-lead ECG, 2 additional 12-lead ECGs will be performed 1 minute apart and the mean of the 3 QTcF values will be calculated. (revised per Amendment 06)

15. Malignant neoplasms within 5 years of Screening (except for basal or squamous cell carcinoma in situ of the skin, or localized prostate cancer in male subjects with treatment cycles completed at least 6 months before Screening). Subjects who had malignant neoplasms but who have had at least 5 years of documented uninterrupted remission before Screening need not be excluded. (revised per Amendment 01)

16. Hypopigmentation conditions (eg, albinism and vitiligo). Hypopigmentation associated with scarring need not be exclusionary

17. Known or suspected history of drug or alcohol abuse or dependence within 2 years before Screening

18. Taking prohibited medications

19. Have participated in a clinical study involving:

- any therapeutic monoclonal antibody, protein derived from a monoclonal antibody, immunoglobulin therapy, or vaccine within 6 months before Screening for whom it cannot be documented that they were randomized only to placebo or never received study drug
- elenbecestat
- any new chemical entity or investigational drug for AD with last study drug dose occurring within 6 months before Screening unless it can be documented that the subject received only placebo (revised per Amendment 06)
- any other investigational medication (unless it can be documented that the subject received only placebo) or device within 8 weeks or 5 half-lives (whichever is longer) before randomization

20. Planned surgery that requires general, spinal or epidural anesthesia that would take place during the study. Planned surgery which requires only local anesthesia and which can be undertaken as day case without inpatient stay postoperatively need not result in exclusion if in the opinion of the investigator this operation does not interfere with study procedures and subject safety.

9.3.3 Removal of Subjects from Therapy or Assessment

The investigator may withdraw the subject from the study at any time for safety or administrative reasons. The subject may stop study drug or withdraw from the study at any time for any reason.

Absolute lymphocyte count from the hematology and differential panel will be monitored during the study. Absolute lymphocyte count will be derived from the CBC with differential representing the normal lymphocytes (with atypical lymphocytes removed and presented as a separate count if they are present) and calculated by the white blood cell count \times percentage of lymphocytes. Should a subject develop a Grade 2 or greater lymphocytopenia (less than $800/\text{mm}^3$), the ALC test should be repeated as soon as possible with the repeat blood sample drawn no later than 5 calendar days from the date of the original test result. If confirmed, study drug administration should be interrupted for a minimum period of 2 weeks and for a maximum period of 4 weeks. Restart of study drug may take place only when ALC returns to greater than $800/\text{mm}^3$. Absolute lymphocyte count will be measured 4 weeks after restart of study drug. Subsequent measurements of ALC will follow the schedule of assessments (Table 5) and any results showing a Grade 2 or greater lymphocytopenia (less than $800/\text{mm}^3$) should be handled as above. If a Grade 2 or greater lymphocytopenia (less than $800/\text{mm}^3$), that is confirmed on repeat testing occurs twice within a 6-month period during the Core Study, then the subject should be discontinued permanently from the study drug. In the Extension Phase, if a confirmed Grade 2 or greater lymphocytopenia (less than $800/\text{mm}^3$) occurs twice from Visit 16 onwards during a 6-month period then the subject should be discontinued permanently from study drug. (revised per Amendments 01, 02, 04, and 06)

Subjects who develop moderate or severe hepatic impairment (eg, Child-Pugh Class B or C) during the study must discontinue study drug. (revised per Amendments 02 and 03) Moderate or severe hepatic impairment are defined as any 2 of the following criteria: INR ≥ 1.7 ; bilirubin $\geq 1.5 \times \text{ULN}$; albumin $< \text{LLN}$; ascites or hepatic encephalopathy. Please note that a single significant abnormality could meet criteria for moderate impairment. (revised per Amendment 03)

Subjects who develop seizures will be discontinued from study drug. (revised per Amendment 03)

In the event that a subject develops a severe infection, study drug administration should be interrupted for a maximum period of 4 weeks. Examples of severe infections include the following: sepsis; deep tissue (invasive) infection; any infection requiring IV antibiotics; any infection requiring hospitalization (if outpatient at onset); any infection leading to need for oxygen, pressors or fluids to support blood pressure, or intubation; any infection that requires major surgical intervention; pseudomembranous colitis due to *C. difficile*; typhlitis; osteomyelitis; and meningitis. Subjects who recover from severe infections within 4 weeks may resume treatment if deemed appropriate by the investigator after consultation with medical monitor. Subjects should permanently discontinue study drug if the severe infection has not resolved within 4 weeks. (revised per Amendment 03)

As described under Dermatologic Assessment in [Section 9.5.1.5.5](#), in the event that a subject develops any skin rash of moderate to severe intensity, or any rash lasting more than 72 hours regardless of severity (with the exception of oral or genital herpes as described in the next paragraph), study drug administration should be interrupted for a maximum period of 4 weeks and a dermatologic consult will be requested regardless of whether the rash is considered drug related or due to other causes. For cases where the investigator suspects a drug rash, regardless of severity, the subject will be discontinued from study drug, a dermatologic consult will be requested, and a skin biopsy will be performed to confirm the diagnosis. The skin rash will be treated as per standard care and will be followed up until resolution regardless of etiology or severity. Subjects who recover from skin rash within 4 weeks may resume treatment if in the opinion of the dermatologic consult, the rash was not drug related and it is deemed appropriate by the investigator after consultation with the medical monitor. Subjects should permanently discontinue study drug if the skin rash has not resolved within 4 weeks or returns during rechallenge. (revised per Amendment 03)

In the event that a subject develops moderate to severe oral or genital herpes, study drug administration should be interrupted for a maximum period of 4 weeks. Subjects who develop a mild case of oral or genital herpes may remain on study drug even if the event lasts more than 72 hours. Subjects who recover from moderate to severe oral or genital herpes within 4 weeks may resume treatment if it is deemed appropriate by the investigator after consultation with the medical monitor. Subjects should permanently discontinue study drug if the oral or genital herpes has not resolved within 4 weeks or returns during rechallenge. (revised per Amendment 03)

Subjects who discontinue study drug early must complete the ED Visit (within 7 days of the last dose of study drug) and the Follow-up Visits (1 and 3 months after the last dose of study

drug). These Follow-up Visits will be conducted to monitor efficacy and safety parameters after early withdrawal from the study or discontinuation of study drug.

For subjects who temporarily suspend study drug (eg, ALC $<800/\text{mm}^3$) but progress to permanently discontinue study drug, the ED and Follow-up Visits should be scheduled as follows: (revised per Amendment 06)

- If ≥ 3 weeks from the last dose, then the ED Visit should be scheduled immediately, and the 1 month Follow-up Visit will not be required
- If < 3 weeks from the last dose, then the ED Visit should be scheduled immediately, and Follow-up Visits at 1 and 3 months after the last dose will be required

All subjects in the Core Study who discontinue study drug before reaching 12 months of treatment will also be asked to return to the clinic for a 12-month clinical assessment and then again at 24 months. Subjects who discontinue treatment between 12 and 24 months of treatment will be asked to return to the clinic for a 24-month clinical assessment. Subjects who discontinue early from study drug are considered “on study” as long as they continue to return for their regularly scheduled clinical assessments at 12 and 24 months as outlined above, at which efficacy and quality of life will be assessed along with concomitant medications. New AEs will be collected for 4 weeks post last dose and followed up for 12 weeks, or until resolution, whichever comes first. AEs relating to study procedures will be collected until the end of study participation. (revised per Amendment 06) However, subjects who discontinue study drug early are not considered to have ‘completed’ the study as a final Subject Disposition.

The primary reason for discontinuation and all other reason(s) contributing to the subject’s discontinuation from study drug(s) should be collected on the ED from study drug eCRF page. In addition, the date of last dose of study drug(s) will be recorded on the Study Drug Dosing eCRF page. If a subject discontinues study treatment and the study at the same time, the end-of-study procedures (Final Visit) will be followed (see [Section 9.5.5](#)).

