9.5.1.3.3 CEREBROSPINAL FLUID SAMPLING

Amyloid CSF is 1 of the 2 methods available for screening to determine subject eligibility for the study. (revised per Amendment 03) Subjects who undergo the eligibility CSF sample collection or who consent to the CSF longitudinal substudy will be encouraged to stay at the site after completion of LP for medical observation. CSF sample(s) will be collected by LP (gravity drip method only) after fasting (preferred), or at least 2 hours after the most recent meal.

CSF samples at Visit 13 should be collected while the subject is still on the study drug and before the other visit assessments. All ED CSF samples need to be taken no later than 7 days

after the last dose of study drug. All CSF samples should be taken at approximately the same time of day as at the Screening Visit. (revised per Amendment 06)

Subjects who provide a CSF sample at Screening for amyloid eligibility purposes, but did not initially consent to the CSF longitudinal substudy may provide consent to the CSF longitudinal substudy at any point in time up to the CSF procedure at Visit 13 (or ED). INR results should be reviewed for subjects who consent to provide a CSF sample and are on concomitant anticoagulation/antiplatelet therapy, before LP; if they are assessed by the investigator to be at risk for bleeding, they are to be excluded from CSF collection. (revised per Amendments 01 and 02)

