An amyloid PET scan may be performed at Screening to confirm deposition of amyloid in the brain. A historical amyloid positive PET scan may be used if conducted within 12 months before the planned date of randomization and provided that the scan and result are considered acceptable by the central PET reading group. As part of an optional substudy, longitudinal amyloid PET imaging will also be conducted after 12 and 24 months of treatment (or at ED, provided the subject has received at least 39 weeks of study drug and at least 6 months has elapsed since the prior amyloid PET scan was performed). (revised per Amendment 04) Longitudinal amyloid PET imaging will only be conducted on subjects that have consented to this optional substudy and who have had Screening amyloid PET scans performed for this study (ie, historical amyloid PET scans cannot be used for the longitudinal analyses).

For subjects participating in the amyloid PET substudy, amyloid PET imaging will be conducted on separate days from the scheduled visits and should be conducted before the clinic Visit 9 and no later than 7 days after the last dose for Visit 13/ED. (revised per Amendment 06)

Descriptions and detailed instructions for all amyloid PET imaging can be found in the PET imaging manual provided to the study PET imaging facilities.

Tau PET (revised per Amendment 05)

A third longitudinal biomarker substudy (tau PET) will be offered to study-eligible subjects from select geographical sites (based on proximity to the tau PET ligand manufacturing sites) in the US who have an amyloid positive study-specific PET scan and who consent to participate in the amyloid PET substudy. For subjects who consent to the tau PET longitudinal substudy, tau PET imaging will be conducted during Screening (after amyloid positive PET results have been reported and before randomization) and again at 24 months (or at the ED Visit, provided the subject has received at least 39 weeks of study drug). At the 24-month timepoint (or at the ED Visit), the amyloid and tau PET scans can be performed in either order, but must be at least 48 hours apart. If the subject has also consented to the longitudinal CSF substudy, the longitudinal substudy assessments can be performed in any order, with at least 48 hours between each procedure.

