For subjects participating in the tau PET substudy, tau PET imaging will be conducted on separate days from the scheduled visits and should be conducted before clinic Visit 13/ED and no later than 7 days after the last dose of study drug. (revised per Amendment 06)

Descriptions and detailed instructions for all tau PET imaging can be found in the tau PET imaging manual provided to the study tau PET imaging facilities that will be in select geographical locations in the US, based on proximity to the tau PET ligand manufacturing sites. (revised per Amendment 05)

Further details regarding pharmacodynamics, pharmacogenomics, and other biomarker research is provided in [Appendix 4](#).

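### When a treatment hold becomes permanent more than 7 days after the last dose, Table 5 orders a lumbar puncture that the protocol's own 7-day CSF limit excludes

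*Protocol*

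**What the plan says.** Protocol Section 9.3.3 sets several temporary holds. A rash that is moderate or worse, or that lasts beyond 72 hours, is held for at most 4 weeks whatever its cause. Severe infection, and oral or genital herpes of at least moderate severity, have the same 4-week maximum. For confirmed low lymphocytes, "study drug administration should be interrupted for a minimum period of 2 weeks and for a maximum period of 4 weeks". On rash it adds: "For cases where the investigator suspects a drug rash, regardless of severity, the subject will be discontinued from study drug". Subjects who recover within 4 weeks "may resume treatment if in the opinion of the dermatologic consult, the rash was not drug related", with the investigator's agreement after consulting the medical monitor. It then says: "Subjects should permanently discontinue study drug if the skin rash has not resolved within 4 weeks or returns during rechallenge". Section 9.5.1.5.5 repeats the rash text.

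A subject who stops outright has the ED Visit within 7 days of the last dose. A subject whose hold becomes permanent follows a separate schedule, added by Amendment 06. If the decision comes at 3 or more "weeks from the last dose, then the ED Visit should be scheduled immediately, and the 1 month Follow-up Visit will not be required". If it comes earlier, the ED Visit is also immediate and both follow-up visits remain.

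The rules for CSF at the ED Visit stand in two places:

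- Section 9.5.1.3.3, tagged Amendment 06: "All ED CSF samples need to be taken no later than 7 days" after the last dose.
- Table 5 footnote y, tagged Amendments 01, 02 and 04: a subject already off drug at the ED Visit is not dosed but still gives CSF. The exemptions are 39 weeks of treatment or less, a CSF sample within 3 months, and a bleeding risk on anticoagulant or antiplatelet therapy.

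The Extension Phase has the same pair. The Assessments text of Appendix 5 gives the 7-day limit, and Table 9 footnote k gives the order to sample without it.

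**The concern.** The CSF rules were written around an ED Visit close to the last dose. The schedule for suspended subjects creates ED Visits well after it, and the footnote that sites work from was not limited to match. A site following Table 5 would perform a lumbar puncture in a subject weeks off drug, for a sample that Section 9.5.1.3.3 excludes. A site following Section 9.5.1.3.3 would depart from the schedule of assessments.

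What is at stake is subject burden. Section 9.2.4 restricts the CSF substudy to one follow-up sample because of what a lumbar puncture asks of the subject. The footnote's only clinical exclusion is bleeding risk, although one reason for a late permanent stop is a severe infection that has not cleared.

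**Working it through.** No sample size, power or alpha figure is involved. The check is a day count from the last dose, followed by a comparison of the rules.

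**Inputs.** Limit for ED CSF: 7 days after the last dose (Section 9.5.1.3.3; Appendix 5). Maximum hold for rash, infection or herpes: 4 weeks = 28 days (Section 9.3.3). Late branch of the suspended-subject schedule: 3 weeks = 21 days (Section 9.3.3).

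**Days past the limit = day of ED Visit - 7.**

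- Outright stop, ED Visit on days 0 to 7: not past the limit. Both CSF rules can be followed.
- Hold made permanent before 3 weeks: within the limit on days 0 to 7, past it on days 8 to 20.
- Hold made permanent at 3 weeks or later: 21 - 7 = at least 14 days past.
- Event unresolved at the end of a full 4-week hold: 28 - 7 = 21 days past.

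The last figure assumes the 4 weeks run from the last dose. Section 9.3.3 does not name the start of the 4 weeks for resolution. If they ran from rash onset and the hold began 72 hours (3 days) later, the decision would fall on day 28 - 3 = 25, which is 25 - 7 = 18 days past. The conclusion is the same.

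A recurrence on rechallenge need not be late, because the last dose is then recent.

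**Do the footnote's exemptions remove the problem?** The 39-week exemption covers early stops only. In the Core Study the only scheduled CSF before Visit 13 is at Screening, so past 39 weeks the 3-month exemption will not normally apply. The bleeding-risk exemption is unrelated to time off drug. For a consenting substudy subject past 39 weeks, the footnote therefore orders the sample on day 21 or day 28, and Section 9.5.1.3.3 forbids it.

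**Extension Phase.** Appendix 5 refers to Section 9.3.3 for its stopping criteria but does not restate the suspended-subject schedule. A hold that has run beyond 7 days nevertheless makes a timely ED Visit impossible, so footnote k and the Appendix 5 limit conflict in the same way.

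**PET for comparison.** ED amyloid PET "should be conducted before the clinic Visit 9 and no later than 7 days after the last dose for Visit 13/ED", and tau PET "should be conducted before clinic Visit 13/ED and no later than 7 days after the last dose of study drug". Table 5 footnotes t and u contain no order to scan a subject already off drug. A late ED Visit simply yields no scan, so there is no matching conflict.

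**The case against.** The best defence is that the CSF rules can be read together. Section 9.5.1.3.3 covers all ED samples and carries the later amendment tag. Footnote y can be taken to describe a subject who stopped a few days before a normal ED Visit: do not dose, but still sample. Sections 9.1.2 and 9.1.2.1 say CSF and PET should be done while the subject is on drug. The superseded Amendment 05 text in the same file placed a one-week maximum beside the same footnote clause. All this stands for ED Visits by day 7, and it shows which rule was probably meant. It does not cover the late visits that Section 9.3.3 now expressly provides for. No text says which rule prevails, and the title of Table 5 itself carries Amendments 05 and 06, so a site has no reason to treat the footnote as out of date.

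The gap between Table 5 footnote b (ED Visit within 7 days for any stop) and Section 9.3.3 is a general rule against a specific exception. That part is editorial and needs only a cross-reference.

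A reader might infer more than the document supports:

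- *The rash rule contradicts itself.* The biopsy to confirm the diagnosis, the route to resumption and the separate use of a permanent stop all point to a provisional stop. Drug stops at once under either word. The text is unclear, not contradictory.
- *The PET limit should be relaxed for late ED Visits.* That is a preference, and it runs against the limit and the on-drug rule that the protocol sets.
- *Late samples would distort the CSF results, or losses would be greater on elenbecestat.* The protocol gives no rate for such stops. Although the multiple-dose study suggested some CD4 reduction at 50 to 100 mg, the protocol links falls near or below the normal limit to 200 and 400 mg, and this trial gives 50 mg.
- *Every lymphocyte hold overruns the limit.* No permanent stop is triggered at the 2-week minimum. The explicit trigger is a second confirmed event within 6 months, where the last dose can be recent.

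**Conclusion.** The point holds in a narrow form. When a temporary hold becomes permanent more than 7 days after the last dose, the schedule tables order a lumbar puncture that the text of the protocol excludes. The overrun is at least 14 days on the 3-week branch and 21 days after a full 4-week hold counted from the last dose. It concerns consenting CSF-substudy subjects past 39 weeks with no CSF in the previous 3 months and no bleeding-risk exclusion.

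How many subjects this affects cannot be derived. The CSF endpoints are set at 24 months in an optional substudy, and the primary CDR-SB analysis is untouched, so the effect on inference is negligible. The puncture in a subject with an active severe infection is a possibility that the wording leaves open, not a documented event. The reason to act is that an invasive procedure with no use under the protocol can be removed with one sentence.

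**What to change.** Add to Table 5 footnote y and Table 9 footnote k: CSF is not collected if more than 7 days have passed since the last dose. In Table 5 footnote b, refer to the Section 9.3.3 schedule for subjects whose hold becomes permanent.

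Optionally, in Sections 9.3.3 and 9.5.1.5.5, state that a suspected drug rash means stopping drug pending consult and biopsy, and that the stop is permanent if drug rash is confirmed. The sponsor should confirm that this is the intent, because a mild, short-lived suspected drug rash currently meets only the sentence on discontinuation.

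The cost is wording in an amendment, with no new data collection. The downside is that ED CSF stays missing for these few subjects, since the efficacy and quality-of-life assessments listed for the 12- and 24-month return visits in footnote b do not include CSF.
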